### Treatment Arms

**Arm A:** Participants assigned to Arm A will engage in CICADAS only for the first 16 weeks of the intervention period. After the completion of the first intervention period and the mid-intervention assessment (V3) visit, these participants will then be assigned to the PEERS only group for the second 16 weeks of the intervention period.

**Arm B:** Participants assigned to Arm B will engage in PEERS + CICADAS for the first 16 weeks of the intervention period. After the completion of the first intervention period and the mid-intervention assessment (V3) visit, these participants will then be assigned to No-Contact (no active intervention) for the second 16 weeks of the intervention period.

**Arm C:** Participants assigned to Arm C will engage in PEERS + Active Control for the first 16 weeks of the intervention period. After the completion of the first intervention period and the mid-intervention assessment (V3) visit, these participants will then be assigned to No-Contact (no active intervention) for the second 16 weeks of the intervention period.

### Treatment Interventions

**CICADAS app:** Participants will complete sensory processing assessments and neuroplasticity-based social cognitive training (NB-SCT) exercises on a digital device for a total of 40 hours through BrainHQ. The CICADAS app captures user-specific sensory processing abnormalities (SPA) through 10 brief computerized assessments. Participants will complete these sensory processing assessments before and after the first intervention period. The data from these assessments guide and personalize the delivery of 13 NB-SCT exercises. The NB-SCT exercises are adaptive with the task difficulty adjusting on a trial-to-trial and session-by-session basis to the abilities of each individual. Participants will need to log in to access these assessments and exercises using a study provided username that contains no personally identifiable information.

| CICADAS Assessments and Training Exercises |                                      |  |                   |
|--|--------------------------------------|--|-------------------|
| Sensory Processing Assessments      |                                      | Neuroplasticity-based Social Cognitive Training Exercises |                   |
| Sound Sweeps                               | Auditory Perception/Processing Speed | That Emotion   | Go/no-go task*    |
| Beep Seeker                                | Auditory Distractor Suppression      | Stop Signal  | Stop-signal task* |

|   |                                      |                       |                              |
|---|--------------------------------------|-----------------------|------------------------------|
| Fine Tuning   | Auditory Distractor Suppression      | Rule Switch           | Set switching task*          |
| Visual Sweeps   | Visual Perception/Processing Speed   | Emotional Faces       | Stroop-like task*            |
| Bubble Pop  | Visual Multiple Object Tracking      | Emotion Tracker       | N-back task*                 |
| Mind Bender   | Visual Task Switching                | Letter Identification | Dot probe task*              |
| Tap The Emotion   | Emotion Detection/Inhibitory Control | Say What?             | Prosody theory of mind task  |
| In the Know   | Auditory Social Memory               | Voice Choice          | Prosody naming task          |
| Face to Face  | Emotion Match/Identification         | Face Replay           | Emotional memory task        |
| Emotional Face  | Emotional Conflict Resolution        | Gaze Match            | Gaze matching task           |
|   |                                      | To-do List Training   | Verbal working memory task   |
|   |                                      | In the Know           | Auditory social memory task  |
|   |                                      | Auditory Ace          | Auditory working memory task |
| *using emotionally expressive faces and emotional valence words |                                      |                       |                              |

**Active Control app:** Participants will play previously-vetted and popular casual video games for an overall duration that is time-matched to the CICADAS program. These games are designed to *not* actively engage the neural systems that underlie ASD. With this kind of control, the current study will be able to assess convergent validity (i.e., that exercises that should improve cognitive function, in fact do) and discriminant validity (that exercises that should not improve cognitive function, in fact don't). We will use control games that are designed to be a face-valid approach to cognitive training, that can be described to participants as a valid approach for improving brain health, and that support a matching of the

expectation-based influence on performance in neuropsychological outcome measures. Participants will also complete the sensory processing assessments before and after the first intervention period.

We will carefully match the CICADAS program and the active control program in overall program use intensity, modality (visual), mode of delivery (supervisor portal), time-spent attending, delivery of rewards, and overall engagement; and provide a comparison group that matches the CICADAS group on the aforementioned attributes, but without the key elements specific to improving the neuro-modulatory control of the brain. Variety and novelty are critical to maintaining participant engagement in the active control group. Here are some examples of the games below:

- Lineup Four: Line up four chips in a row before your opponent.
- Bricks Squasher II: Move a paddle and bounce the ball to destroy the bricks.
- Gems Swap: Form a line of 3 or more identical gems by swapping their positions.

These computer games are fully developed, widely believed to be cognitively beneficial, are applied in graded levels in training, and are rated E (for everyone) by the Entertainment Software Rating Board.

**PEERS:** Participants will be asked to attend weekly 1-hour group sessions led by a PEERS clinician. Each PEERS group session will consist of a minimum cohort of 3 participants and will meet as a group during the 16 week period either remote and/or in-person. The PEERS clinician will create a video-conferencing room open to cohort participants who meet remotely using Zoom application. The group sessions will be scheduled and monitored by the PEERS clinician. PEERS teaches how to solve real-life social dilemmas, appraise affect and social contexts, and initiate and maintain conversations while receiving feedback from peers and clinicians. Additionally, structured practice interactions during socialization activities (e.g., playing sports, games, etc.) are integrated into the curricula. Adjustments may be made during COVID-19 to allow for a more appropriate treatment given current shelter-in-place and distance-learning procedures that may not allow for replication of the traditional protocol.

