## General Study Design

We will employ a three-arm, active-controlled, randomized crossover trial to assess the safety and efficacy of CICADAS app in adolescents with ASD, and to evaluate its potential as a stand-alone treatment, as a primer for PEERS, or as a treatment enhancer of PEERS. We will randomize adolescents with ASD (ages 11-18) to CICADAS only, PEERS + CICADAS app, or PEERS + Active Control app.

Approximately 56 participants will be consented to ensure the successful completion of 48 participants (16 participants per treatment arm). A diagnostic interview will be performed to determine eligibility. Following inclusion and enrollment, participants will complete a set of assessments prior to the intervention to establish their baseline performance. Participants will then be randomized to the CICADAS only group (Arm A), PEERS + CICADAS app group (Arm B), or PEERS + Active Control app group (Arm C) and spend up to 16 weeks engaged in their assigned intervention. After 16 weeks, a full battery of assessments will be administered. For the next 16 weeks, Arm A will continue with PEERS only and Arms B and C will receive no treatment during this period. At the end of the intervention period, a full battery of assessments will be administered a second time to evaluate changes in performance. Finally, participants will be asked to fill out an online exit survey to rate enjoyment, usability, perceived benefits, and ease of fit into schedule.

During the first intervention period, participants assigned to the CICADAS only will complete NB-SCT exercises for 16 weeks. Participants assigned to PEERS + CICADAS will engage with the CICADAS app and complete weekly 1-hour PEERS group sessions for 16 weeks. Participants assigned to receive the PEERS + Active Control will engage in the Active Control app and complete weekly 1-hour PEERS group sessions for 16 weeks. During the second intervention period, participants assigned to receive PEERS only will complete weekly 1-hour PEERS group sessions for 16 weeks. During both intervention periods, these participants may have weekly electronic check-ins with site study personnel (as needed). The CICADAS app and the Active Control app icons, design and user experience will look the same as to not unblind the participants.

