## Sample Size Justification

Attrition rates from the ASD pilot study conducted at University of Minnesota were > 30%. This high dropout rate can be ascribed to design issues, in that: (1) the sample recruited for the pilot consisted of adolescents who were not intrinsically interested in long-term treatment options for ASD, unlike the current target (adolescents already seeking PEERS); and (2) study coordinators had not been formally trained on how to keep participants engaged in a remote cognitive training intervention. By recruiting adolescents already seeking PEERS and by rigorously training our staff, we expect retention rate for this project to be in line with those of 1) cognitive interventions delivered to adolescents with ASD; 2) PEERS groups. We project a 15% non-completion rate estimate for this study. We will recruit 56 participants to obtain 48 study completers. As the primary aim of this study is to gather information about the feasibility, acceptability and usability of this approach, the sample size of N=56 is set primarily for practical reasons and not driven by hypothesis testing. This size will, however, provide data to power a subsequent pivotal efficacy trial in Phase II, and will provide the field validation data required to submit CICADAS to the FDA as a medical device for such a trial

under the 510k de novo process. We are confident that we will meet our recruitment goals with these resources in place.

Of interest to the design of our proposed trial, despite randomization to the auditory or visual training conditions, 73.2% of participants who were assigned to the Visual condition at BL completed the training whereas only 38.5% of participants who were assigned the Auditory Condition completed the program. This highlights the importance of personalized intervention programs that take individual differences (e.g., auditory sensitivity) into consideration. In fact, several participants who chose to discontinue attributed their decision to an aversion to the auditory stimuli used in the computer programs. Baseline SCAN Competing Words Test scores were significantly related to whether individuals randomized to the Auditory or Visual NB-SCT Modules completed their training [ $F(2,23) = 6.331, p = .006$ ]. In other words, participants randomized to the Auditory NB-SCT who did not complete their program had significantly more auditory processing difficulties than those who completed the program.

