With 48 participants fully evaluated, we will not have enough power to detect a treatment augmentation effect ascribable to CICADAS. However, data from this pilot trial will be used to power a pivotal RCT in Phase II, as they will allow to explore whether:

- a) the concurrent delivery of CICADAS and PEERS for 16 weeks (B1-B2) induces greater improvements sensory processing, cognition, symptom reduction, social skills and behaviors, as well as quality of life, compared to CICADAS only (A1-A2) or PEERS + Active Control (C1-C2) – *preliminary efficacy of CICADAS as a treatment enhancer for PEERS*;
- b) The concurrent delivery of CICADAS and PEERS for 16 weeks (B1-B2) induces greater improvements sensory processing, cognition, symptom reduction, social skills and behaviors, as well as quality of life, compared to the sequential delivery of CICADAS and PEERS (A1-A3) – *preliminary testing of CICADAS as enhancer vs primer*;
- c) improvements sensory processing, cognition, symptom reduction, social skills and behaviors, and quality of life induced by the concurrent delivery of CICADAS and PEERS (B1-B2) are sustained after 16 weeks of no contact (B2-B3) – *durability of augmentation effects*.

To verify these experimental hypotheses, we will conduct the analysis based on the pre-intervention (baseline) and post-intervention data. The criterion for statistical significance is  $p < 0.05$ . Results with  $p < 0.1$  will be described as trends.

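### The Active Control arm cannot show that the games leave cognition unchanged: they are given only with PEERS, and no equivalence criterion is set

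*Protocol*

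**What the plan says.** **The claim.** Protocol, Treatment Interventions, Active Control app: "With this kind of control, the current study will be able to assess convergent validity". The same sentence then adds "discriminant validity (that exercises that should not improve cognitive function, in fact don't".

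**Who receives the games.** Protocol, Treatment Arms: "Participants assigned to Arm C will engage in PEERS + Active Control for the first 16 weeks of the intervention period". No other arm receives them, and in the second period Arm C has no active intervention.

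**Size.** Protocol, General Study Design: "Approximately 56 participants will be consented to ensure the successful completion of 48 participants (16 participants per treatment arm". Under Sample Size Justification, "the sample size of N=56 is set primarily for practical reasons and not driven by hypothesis testing".

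**Analysis.** The SAP (Secondary Outcome - Preliminary Efficacy) uses a linear mixed model whose key significance test is the interaction of group and time. It adds within-group Cohen's d computed from change scores. The threshold is p<0.05, and p<0.1 is labelled a trend. Exploratory question (a) compares Arm B with Arm C, and with Arm A, from baseline to mid-study, with cognition among the outcomes. On power the SAP says "we will not have enough power to detect a treatment augmentation effect ascribable to CICADAS". Neither document gives an equivalence margin, an equivalence test, or an analysis aimed at the games themselves.

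**The concern.** The clause says what is to be concluded about the games: that they do not improve cognitive function. A conclusion of no effect needs two things. The effect of the games must be separable from everything else the arm receives, and the estimate must be precise enough to exclude an effect that matters, against a margin fixed in advance. The plan provides neither.

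At stake is how the control arm is read. If Arm C changes little, the Protocol's sentence invites the reader to treat the games as shown to be inert, and so to read any CICADAS result against a neutral background. The Protocol itself notes that many people believe these games help cognition, so inertness cannot simply be presumed. The data are also meant to inform a Phase II pivotal trial, so the limits of the control should be stated accurately.

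**Working it through.** **Step 1. The plan's own figures.** Protocol, Sample Size Justification: "We will recruit 56 participants to obtain 48 study completers" and "We project a 15% non-completion rate estimate for this study".
- 48 / 3 = 16 completers per arm, as stated.
- 48 / 0.85 = 56.5, against the stated 56, and 56 × 0.85 = 47.6. The figures agree to rounding, and nothing below depends on the difference.
- If everyone recruited is randomised and contributes data, 56 / 3 gives 18 to 19 per arm.

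**Step 2. Can any arm isolate the games?** Weeks 0 to 16, from Treatment Arms:

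| Arm | PEERS | App |
|---|---|---|
| A | no | CICADAS |
| B | yes | CICADAS |
| C | yes | games |

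- Change within C combines games, PEERS, practice and maturation. Alternate test forms are used only where they exist (Protocol, Assessments), so some retest gain may remain.
- C against B differs in the app alone, but the comparator is CICADAS rather than no app.
- C against A differs in both the app and PEERS.
- In the Protocol, the only period of PEERS without an app is Arm A's weeks 16 to 32. It is not concurrent with the games and follows CICADAS. The SAP (Statistical Plan) describes that same period as no contact for all three arms. The two texts must be reconciled, but neither supplies a comparator for the games.

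No contrast gives the effect of the games, and a larger sample would not change this.

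**Step 3. Precision of Arm C's change.** Assumptions: two-sided 95% interval, since the SAP does not state sidedness, and units of the change-score SD, since neither document gives an SD for cognition. These are also the units of the SAP's within-group Cohen's d.
- Half-width = t(0.975, n−1) / √n.
- n = 16: 2.131 / 4 = 0.53 SD.
- n = 18 to 19: 0.50 to 0.48 SD.

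An observed change of zero would have an interval of about −0.53 to +0.53 SD.

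**Step 4. Precision of B minus C.** Simple difference in mean change, equal SDs.
- Half-width = t(0.975, 2n−2) × √(2/n).
- n = 16 per arm: 2.042 × 0.354 = 0.72 SD.
- n = 18 to 19 per arm: 0.68 to 0.66 SD.

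**Step 5. What an equivalence test would have needed.** The margins here are assumed, because the documents give none. Two one-sided 5% tests, true effect zero, simulated power with 16 in Arm C:

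| Margin (SD) | Power, Arm C change | n for 80% power, one group |
|---|---|---|
| 0.2 | 0% | 215 |
| 0.3 | 0.4% | 96 |
| 0.5 | 24% | 35 |
| 0.8 | 84% | not computed |

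The n column uses ((z(0.95) + z(0.90)) / margin)². At 0.5 SD this is (2.926 / 0.5)² = 34.3, so 35. Against a hypothetical concurrent PEERS-only arm of 16, power at a 0.5 SD margin would be about 1%. Eighty per cent power would need 2 × 34.3 = 68.5, so 69 per arm.

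**The case against.** The strongest reply is that the sentence is design rationale and not a hypothesis. It speaks of assessing, not proving. It pairs convergent with discriminant validity and goes on to describe a matched comparison group, so it can be read as meaning only that CICADAS should do better than games. Discriminant validity appears neither among the primary measures nor in exploratory questions (a) to (c). Question (a) already specifies B against C, in which PEERS, practice and maturation balance in expectation.

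Much of this stands. It is why the point is minor, and why the remedy builds on a contrast that is already planned. It does not rescue the clause. B could exceed C while the games also help, and B could equal C because both help or neither does. The power disclaimers concern hypothesis testing in general and the CICADAS augmentation effect. Neither qualifies the statement about the games.

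Two stronger readings are tempting, and the documents do not support them.
- A reader might infer that the claim will rest on a significance test of Arm C's change. Such a paired test at n = 16 has power 0.465 for a 0.5 SD gain, and so would miss it about 53% of the time. The SAP plans no within-arm test, only the interaction and within-group Cohen's d. That miss rate does not describe a planned analysis.
- A reader might infer that the sponsor will report a flat Arm C as proof that the control is inert. No planned report says so. The documents call the efficacy evidence preliminary.

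**Conclusion.** The concern holds as a point about one claim. The trial cannot establish that the control games do not improve cognition. The main reason is structural: the games are never separated from PEERS by any concurrent comparison. The second is precision: with about 16 completers, Arm C's change is known to within about ±0.53 change-score SD, and no margin is set against which to judge it. The planned B minus C contrast remains interpretable as CICADAS relative to games on top of PEERS, with a half-width of about 0.72 SD.

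The half-widths assume two-sided 95% intervals, 16 completers per arm, equal SDs and simple change scores. A covariate-adjusted mixed model may differ somewhat. Using all 56 participants narrows the intervals only slightly. The structural reason needs none of these assumptions. No primary outcome, population or sample size is affected.

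**What to change.** - **Protocol, Treatment Interventions, Active Control app:** delete the clause saying the study can assess that the control exercises do not improve cognition. State instead that Arm C controls for app exposure alongside PEERS.
- **SAP, exploratory question (a):** state that specificity is described only by the B minus C difference in week 0 to 16 change on the cognition measures, reported with its 95% confidence interval.
- **SAP, same section:** state that a small or non-significant change in Arm C, including a small within-group Cohen's d, will not be read as evidence that the games have no effect.

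**Cost:** wording in two documents, with no change to arms, visits, sample size or planned model. The validation that the trial can claim becomes narrower.

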#### *Application Security*

**CICADAS and Active Control apps:** All usage and progress data collected through the CICADAS and Active Control applications are encrypted then transmitted to a central server. Data is encrypted in transit and at rest, and access is limited and audited. Data collected through the platform will not include geographic information. IP address data is stored only in memory and in request logs, and is used for technical support and troubleshooting, but not persisted with the participant's data. However, data as it relates to dates that assessments are completed is collected and stored. On the server, the data are available for review by the unblinded members including, site study coordinator, Posit Science study team, and/or other

study personnel, through a secure web portal. The study team in particular will use the secure web portal to regularly check on usage and progress of each active participant to customize their weekly phone/in-person to provide helpful guidance and coaching.

**Zoom:** This platform allows participants to communicate with others via the app without having to share their full name, mobile phone number or email to do so. Participants will choose whether to use their first name or an alias. In order to access the Zoom meeting, participants will be required to enter a passcode for their specific meeting. Once the participants enter the meeting, they will be operating within the Zoom HIPAA-compliant digital environment, and data that are produced, transmitted, and shared among users will be exclusively visible/readable to other participants and study staff. These data will include personally identifiable information—such as faces, first names or aliases, biographical and medical information—similar to what happens during all in-person group therapy sessions. Participants will be aware that the research team will have access to the group chat history and will be monitoring its contents throughout the intervention periods. As such, participants are informed that any personally identifying information voluntarily shared on this platform will be viewed by study staff. More information about how Zoom protects privacy can be found here:

<https://zoom.us/en-us/trust/privacy.html>

